**Appendix 5 DAS28 and EULAR Response Criteria**

**DAS28** is a formula combining:

- Tender Joint Count (28 joints)
- Swollen Joint Count (28 joints)
- ESR (mm/hour) or CRP (mg/L)
- General Health - Patient's Global Assessment of Disease Activity (VAS)

$$\text{DAS28-CRP} = [0.56 \times \sqrt{(\text{TJC28})} + 0.28 \times \sqrt{(\text{SJC28})} + 0.36 \times \log_{\text{nat}}(\text{CRP}+1)] \times 1.10 + 1.15$$

A calculator is available online at the following website:

<http://www.das-score.nl/das28/DAScalculators/dascalculators.html>

A representation and example is given below:

Based on the DAS28 score, disease activity is classified as:

≤ 2.6	Remission
>2.6 ≤ 3.2	Low disease activity
>3.2 ≤ 5.1	Moderate disease activity
>5.1	High disease activity

**EULAR response Criteria:**

Based on the DAS, response criteria have been developed, the EULAR response criteria. The EULAR response criteria include not only change in disease activity but also current disease activity. To be classified as responders, patients should have a significant change in DAS (at least >0.6 from Baseline) and also low current disease activity. Three categories are defined: good, moderate, and non-responders.

The EULAR response criteria using the DAS28			
	Improvement in DAS28 from Baseline		
DAS28 at endpoint	> 1.2	>0.6 and ≤1.2	≤0.6
≤3.2	Good	Moderate	None
> 3.2 and ≤5.1	Moderate	None	None
> 5.1	Moderate	None	None

## Modification History

Unique Identifier for this Version	Date of the Document Version	Author	Significant Changes from Previous Authorized Version
V1.0	28Dec2017		Not Applicable – First Version
Draft V1.01	12Jul2018		
 
1. Updated protocol version from amendment 05 (dated 19Oct2017) to amendment 04 (dated 27Apr2017), as Archigen decided to revert protocol version for the study.
 
2. Removed all Part C and extension study due to protocol version revert.
 
3. Updated unit of duration of MTX from weeks to months.
 
4. Updated planned dose intensity from “133.3334 mg/day for subjects who completed both infusions of the course” to “Planned Dose Intensity for every course (mg/day) = 2000 mg/15 days = 133.3334 mg/day for subjects who completed both infusions for the course.in Part A or Part B, and for subjects who only received for the first administration in Part A or Part B, subjects’ planned dose intensity will be 1000 mg/1 day = 1000 mg/day” in section 12.1.
 
5. Removed the extreme studentized deviate test from detecting outliers.
 
6. Updated formula of DAS28-ESR from “<math>0.56 \times \sqrt{(TJC28)} + 0.28 \times \sqrt{(SJC28)} + 0.7 \times \ln(ESR+1) + 0.14 \times GH</math>” to “<math>0.56 \times \sqrt{(TJC28)} + 0.28 \times \sqrt{(SJC28)} + 0.7 \times \ln(ESR) + 0.014 \times GH</math>”
 
7. Added detail and SAS code (Appendix 4) for multiple imputation for missing at random in section 15.1.4.
 
8. Added reference and SAS code (Appendix 5) for logistic regression described in section 15.2.3.
 
9. Added detail for definition of baseline in section 5.2, i.e. “For joint assessments, patient’s global assessments, physician’s global assessments, CRP and ESR, both date and time will be considered for defining baseline.”.
 
10. Updated definition of depletion of CD19+ B cell count to “CD19+ B cell count below the
 

Document: \\eedc-vnasc01\Biosdata\Archigen\SAIT101\YWA21301\Biostatistics\Documentation\SAP  
 Author: Version Number: V2.0  
 Version Date: 13Feb2019

Template No: CS\_TP\_BS016 Revision 4  
 Effective Date: 01Apr2016

Reference: CS\_WI\_BS005

			
limit of quantification (20 cells/<math>\mu</math>L)” due the assay limit of 20 cells/ <math>\mu</math>L/
 
11. Updated PKAS to only include subjects with at least one primary PK parameter
 
12. Updated handling of BLQ values prior to <math>C_{max}</math>; BLQ values are set to missing rather than setting BLQ values prior to <math>C_{max}</math> to zero, which is more applicable for oral dosing, where a lag time for detection of quantifiable concentrations may be observed.
 
13. Added rules for exclusion of PK parameters
 
14. Updated handling of missing data for Change from Baseline calculation of CD19+ B cell counts

Draft v1.02	07Sep2018		
Section 3.1: Added “Other analyses may be added in case they’re thought to affect DSMB safety review, however no statistical inference will be included in order to avoid an inflation of the type I error.”, “DSMB4 will include all safety analyses and immunogenicity and PK/PD without any statistical inference.”
 
Section 5.2: Added vital sign for considering both date and time while defining baseline
 
Section 9: Updated wording for HAQ-DI categories
 
Section 15.1.2: Added medical review for potential outliers and outliers will be confirmed during blinded data review meeting prior to database lock and unblinding

Draft v1.02	27Dec2018		
Section 8: Per sponsor comments on dry run delivery, added specification of “adequate response” and “inadequate response” for analysis by Week52, i.e. adequate response: met all eligibility requirements for retreatment, which will be captured from “Re-treatment” of CRF
 
Section 8-Completed of Part B: added detail to clarify, i.e. required to receive complete study treatment of Part B
 
Typo revision of “captured”

Draft v1.03	15Jan2019		
Removed DSMB4 and W24 CSR.
 
Section 2.6 updated.
 
Section 3.2 and 3.3: Updated Analysis for Week 24 CSR (Part A) and for Week 52 CSR (Part B) into one final analysis, due to W24 CSR

Document: \\eedc-vnasc01\Biosdata\Archigen\SAIT101\YWA21301\Biostatistics\Documentation\SAP  
 Author: Version Number: V2.0  
 Version Date: 13Feb2019

Template No: CS\_TP\_BS016 Revision 4 Reference: CS\_WI\_BS005  
 Effective Date: 01Apr2016

			
canceled and no unblinded at W24.
 
Section 4.3-FAS: Per agreement during blinded data review meeting 1, omit criteria of eligible for Part A or not while excluding patients from the FAS.
 
Section 4.5-PP: Per agreement during blinded data review meeting 1, if patients who were ineligible for Part A, they will be excluded from the PP set.
 
Section 9: added tables for baseline characteristics by site 10703 and other sites.
 
Section 13.2: Added two impact analyses added.
 
Section 15.2.2 adjustment of ESR: If ESR=0, it will be adjusted as <math>\ln(\text{ESR}+1)</math> while calculating DAS28-ESR, i.e. <math>\ln(1)=0</math>
 
Section 15.3.3: added line chart for changes from baseline of DAS28-CRP and bar chart for ACR20/50/70, which already existed in SHELL.
 
Section 15.3.3.: added above two figures for site 10703 per sponsor request.
 
Section 15.2.7: an impact analysis was added for site 10703 to evaluate impact of the site on the main efficacy analysis.

Draft 1.04	31Jan2019		
Section 4.5: Updated definition of PP set and omitted PP2 set.
 
Section 8: Updated disposition summary per agreement on BDR1 meeting
 
Section 15.2.5: Added comparison for MabThera vs Rituxan as one of exploratory analysis
 
Section 15.2.6: Removed sensitivity analyses due to protocol deviation
 
Section 15.2.7: had been adjusted to 15.2.6 in main context
 
Section 16.1: Updated definition of TEAE, i.e. no limit of end date
 
Section 11.1 and Appendix 1: prior and concomitant are derived by answer of CRF (Was the medication/therapy taken prior to the study? Yes=prior, No=concomitant)

Draft 1.05	12Feb2019		
Section 2.6: Added immunogenicity analyses.
 
Section 4: Added clarification for PK and PD analysis sets.
 
Section 9: Updated analysis for demographic and other baseline characteristics for overall

Document: \\ieedc-vnasc01\Biosdata\Archigen\SAIT101\YWA21301\Biostatistics\Documentation\SAP  
 Author: Version Number: V2.0  
 Version Date: 13Feb2019

Template No: CS\_TP\_BS016 Revision 4 Reference: CS\_WI\_BS005  
 Effective Date: 01Apr2016

			
total (Site 10703/ All sites except site 10703/ Overall)
 
Section 15: Added description for all three comparisons (SAIT101 vs MabThera®, SAIT101 vs Rituxan®, MabThera® vs Rituxan®) for efficacy endpoints per sponsor request.
 
Section 15.2.5: Updated sentence to make it clear.
 
Section 17: Added analysis of proportion, 95%CI, difference, 95%CI for difference per sponsor request.

2.0	13Feb2019		
Section 15.1.2: Added detail, i.e. "If there are any confirmed outliers, then analysis will be performed with and without the outlier(s) to see how the outliers affect study results as sensitivity analysis after unblinding. If there is no confirmed outlier, then box plot and the sensitivity analysis will not be performed after unblinding for final analysis."

---

Document: \\ieedc-vnasc01\Biosdata\Archigen\SAIT101\YWA21301\Biostatistics\Documentation\SAP  
 Author: Version Number: V2.0  
 Version Date: 13Feb2019

Template No: CS\_TP\_BS016 Revision 4 Reference: CS\_WI\_BS005  
 Effective Date: 01Apr2016

## 1. Introduction

This document describes the rules and conventions to be used in the presentation and analysis of pharmacokinetics (PK), efficacy, safety, pharmacodynamics (PD), and immunogenicity data for Protocol AGB001. It describes the data to be summarized and analyzed, including specifics of the statistical analyses to be performed. The following analyses will be performed for this study analysis for third data and safety monitoring board (DSMB) analysis and additional if needed, analysis for period till Week 52 (Week 52 CSR).

This statistical analysis plan (SAP) is based on protocol version amendment 04, dated 27Apr2017.

## 2. Study Design and Study Objective

### 2.1. STUDY OBJECTIVE

#### 2.1.1. PRIMARY OBJECTIVE

The primary objective of the study is to compare the PK of SAIT101 versus rituximab licensed in the European Union (hereafter designated MabThera®, brand name in EU) versus rituximab licensed in the United States (hereafter designated Rituxan®, brand name in US) in patients with rheumatoid arthritis (RA).

#### 2.1.2. SECONDARY OBJECTIVE

The secondary objectives of the study are to compare the safety, additional PK, PD, efficacy, tolerability, and immunogenicity of SAIT101 versus MabThera® versus Rituxan® in patients with RA.

### 2.2. STUDY DESIGN

This is a multicenter, randomized, double-blind and parallel group study in patients with RA. It consists of Part A up to 24 weeks followed by Part B up to Week 52 that also collects transition data in patients eligible for a second course of treatment.

[figure not shown]
The regular study duration of the study per individual patient will be 52 weeks from the start date of the first course. To prevent missing data in important supportive efficacy and safety analysis, patients who discontinued study treatment, will also attend all visits until Week 52.

It is planned to randomize approximately 282 patients at approximately 70 investigative centers globally.

---

Document:	\\ieedc-vnasc01\Biosdata\Archigen\SAIT101\YWA21301\Biostatistics\Documentation\SAP	Version Number:	V2.0
Author:		Version Date:	13Feb2019
Template No:	CS_TP_BS016 Revision 4	Reference:	CS_WI_BS005
Effective Date:	01Apr2016		

Figure 1. Study Design from Protocol

### 2.3. SAMPLE SIZE CALCULATION

A percentage co-efficient of variation (CV%) ranging from 26.3 to 37.3% for the five co-primary parameters is assumed for this study based on a recent study in RA patients treated with rituximab.

When the evaluable sample size in each group is 84, a three group design will have 81% power to reject both the null hypothesis that the ratio of test to standard geometrics means is below 0.800, and the null hypothesis that the ratio of test to standard geometrics means is above 1.250 (i.e., that the test and standard are not equivalent), in favor of the alternative hypothesis, that the means of the two groups are equivalent, assuming that the expected ratio of means is 1.000, the CV% for the standard is 0.330, that data will be analyzed in the log scale using analysis of variance (ANOVA) and that each one sided test is made at the 5% level. Each of the 15 hypotheses tests (five co-primary endpoints × three pairwise comparisons) are powered at 98% to 99.0% to yield 81% study-wide power.

Approximately 282 patients (94 patients per group) will be randomized in order to yield a minimum of 84 patients per group to account for a presumed 10% withdrawal.

These 94 patients in SAIT101 group and MabThera® group will provide 96% probability of declaring the equivalence in FAS with each one-sided test at the 2.5% level, accounting for a presumed 1.0 standard deviation (SD) of DAS28 from the REFLEX study, and the equivalence margin of -0.6 to 0.6 chosen as the half of a clinical meaningful improvement of 1.2 in DAS28. Considering 18% withdrawal from the REFLEX study, approximately 77 patients per group will provide approximately 91% probability of declaring the equivalence in the Per Protocol (PP) set.

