## 6 STATISTICS

### 6.1 Sample Size

The PK parameters reported from a recent study with rituximab in patients with RA revealed a percentage coefficient of variation (CV%) ranging from 26.3% for  $C_{\max}$  to 37.3% for  $AUC_{0-\infty}$ .

When the evaluable sample size in each group is 84, a three group design will have 81% power to reject both the null hypothesis that the ratio of test to standard geometrics means is below 0.800, and the null hypothesis that the ratio of test to standard geometrics means is above 1.250 (i.e., that the test and standard are not equivalent), in favor of the alternative hypothesis, that the means of the two groups are equivalent, assuming that the expected ratio of means is 1.000, that data will be analyzed in the log scale using analysis of variance (ANOVA) and that each one sided test is made at the 5% level. Each of the 15 hypotheses tests (five co-primary endpoints  $\times$  three pairwise comparisons (i.e., SAIT101 vs. MabThera®, SAIT101 vs. Rituxan®, MabThera® vs. Rituxan®)) are powered at 98% to 99.0% to yield 81% study-wide power.

Approximately 282 patients (94 patients per group) will be randomized in order to yield a minimum of 84 patients per group to account for a presumed 10% withdrawal.

This 94 patients in SAIT101 group and MabThera® group will provide 96% probability of declaring the equivalence in FAS with each one sided test at the 2.5% level, accounting for a presumed 1.0 standard deviation of DAS28 from the REFLEX study, and the equivalence margin of -0.6 to 0.6 chosen as the half of a clinical meaningful improvement of 1.2 in DAS28. Considering 18% withdraw from the REFLEX study, approximately 77 patients per group will provide approximately 91% probability of declaring the equivalence in the PP set with the same above assumption.

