## 6.2. MULTIPLE COMPARISON/MULTIPLICITY

No multiple comparison adjustment will be used for main efficacy analysis, since there is only one main efficacy analysis for change from baseline at Week 24. No multiple comparison adjustment will be used either for the PK analyses since the significance level is pre-specified at 10% (two-sided) to show equivalence within pre-specified limits, and the overall power for the PK equivalence assessment accounts for the multiple testing.

---

Document: \\ieedc-vnasc01\Biosdata\Archigen\SAIT101\YWA21301\Biostatistics\Documentation\SAP  
Author: Version Number: V2.0

Version Date: 13Feb2019

Template No: CS\_TP\_BS016 Revision 4  
Effective Date: 01Apr2016

Reference: CS\_WI\_BS005

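### At the stated CV of 0.330, 84 patients per group give about 93% study-wide PK power, not the 81% printed in SAP 2.3 and the protocol synopsis

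*SAP*

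**What the plan says.** SAP 2.3 opens with a CV "ranging from 26.3 to 37.3% for the five co-primary parameters is assumed for this study". It continues: "When the evaluable sample size in each group is 84, a three group design will have 81% power". The inputs listed for that power are an expected ratio of 1.000, limits of 0.800 and 1.250, log-scale ANOVA, each one-sided test at 5%, and "the CV% for the standard is 0.330". It then says that the 15 tests (five co-primary endpoints by three pairwise comparisons) "are powered at 98% to 99.0% to yield 81% study-wide power". The Sample Size part of the protocol synopsis makes the same statement, including the 0.330.

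Protocol 6.1 keeps the 84, the 98% to 99.0% and the 81%, but its inputs differ. It cites "a percentage coefficient of variation (CV%) ranging from 26.3% for" Cmax up to 37.3% for AUC0-inf, and then proceeds "assuming that the expected ratio of means is 1.000, that data will be analyzed in the log scale", with no 0.330. It gives no CV for AUC0-t, AUC0-d15 or Ctrough. None of the three places says how the per-test powers were combined.

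SAP 6.2 refers back to the result when it explains why the PK tests are not adjusted: "the overall power for the PK equivalence assessment accounts for the multiple testing".

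**The concern.** SAP 2.3 and the synopsis supply everything needed to recompute the power, and the answer differs from the printed one. This is the only power statement for the primary objective. If 0.330 is the real input, overall power is understated by about 12 points. If the design rests on CVs near the top of the 26.3% to 37.3% range, 0.330 is misleading and the margin it suggests is not there. A reader cannot tell which applies, because three of the five CVs are not printed. SAP 6.2 relies on the same figure.

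**Working it through.** **Inputs.** From SAP 2.3: n = 84 evaluable per group, ratio 1.000, limits 0.80 and 1.25 (±ln 1.25 = ±0.2231), one-sided 5%, 15 tests, CV 0.330. From Protocol 6.1: 26.3% for Cmax and 37.3% for AUC0-inf. The 0.330 is labelled a percentage but is read here as 33.0%.

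**1. The plan's own step from per-test to overall power.** 0.81^(1/15) = 0.986, which lies inside the printed 98% to 99.0%. At the ends, 0.98^15 = 0.739 and 0.99^15 = 0.860. So the printed pair of figures fits a simple product of 15 powers of about 98.6%.

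**2. Per-test power at CV 0.330.**
- Log-scale SD = sqrt(ln(1 + 0.330²)) = 0.3215.
- SE of a difference = 0.3215 × sqrt(2/84) = 0.0496.
- Normal approximation: 2Φ(0.2231/0.0496 − 1.645) − 1 ≈ 0.9957; to the 15th power, 0.937.
- Exact power of the two one-sided tests, integrating over the variance estimate (df = 166): 0.9954; to the 15th power, 0.933. With variance pooled over three arms (df = 249) the product is 0.935.

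**3. Could correlation among the tests explain 81%?** The probability that all 15 pass is at least 1 − 15 × (1 − 0.9954) = 0.931 under any dependence. Simulating three shared arms and five endpoints (df = 249) gives 94%, 95% and 96% for endpoint correlations of 0, 0.5 and 0.8. Correlation moves the result away from 81%.

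**4. Other readings of 0.330.** Taken as the log-scale SD, it gives 0.906. One-sided 2.5% tests give 0.834, but the text states 5%. Limits of ±0.20 on the log scale give 0.764, but the text states 0.80 to 1.25.

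**5. The CV that the printed figures imply** (exact, df = 166, n = 84):

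| Common CV | Per test | Product of 15 |
|---|---|---|
| 0.263 | 0.9999 | 0.999 |
| 0.330 | 0.9954 | 0.933 |
| 0.362 | 0.9861 | 0.810 |
| 0.373 | 0.9810 | 0.750 |

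Per-test power of 99.0% to 98.0% corresponds to CVs of 0.351 to 0.375, so 0.330 lies outside the range that the paragraph's own per-test figures imply. At CV 0.330, 71 per group already give 0.9865 per test and a product of 0.816.

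**6. Using the two CVs in Protocol 6.1.** Hold Cmax at 26.3% and AUC0-inf at 37.3%, with three tests per endpoint. The other three CVs are assumptions:

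| Other three endpoints | Product of 15 |
|---|---|
| all at 37.3% | 0.9999³ × 0.9810¹² = 0.794 |
| one at 33%, two at 37.3% | 0.830 |
| two at 33%, one at 37.3% | 0.867 |
| all at 33% | 0.906 |

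A product of 0.81 needs the three at a common CV of about 0.369 (0.983 per test). For the first row, joint simulation with shared arms gives 82%, 84% and 89% at assumed endpoint correlations of 0, 0.5 and 0.8. At 26.3% each Cmax test has 99.99% power, so the statement that each of the 15 tests lies at 98% to 99.0% cannot be right either.

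**The case against.** The strongest reply is that 0.330 is one stray number. Every version of the calculation also cites the 26.3% to 37.3% range, and Protocol 6.1, the full sample-size section, does without 0.330. From the upper end of the range, 81% is about right: with Cmax at 26.3% and the rest at 37.3%, it is 79% by product and 82% with shared arms and independent endpoints. Deleting 0.330 would remove the outright contradiction. That stands, but the text would still not show which CVs produced 81% or how the tests were combined.

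It is also fair that 0.362 depends on the product rule and a common CV. Allowing for shared arms raises it to about 0.366 with uncorrelated endpoints and about 0.374 with endpoint correlation 0.5. The product rule is used here because it fits the plan's own step from 98.6% to 81%. The finding at 0.330 does not depend on that choice.

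The consequence for SAP 6.2 is limited. Protocol 6.3 requires every pair on every primary endpoint to pass, and that does not inflate the type I error whatever the power. The decision not to adjust is unaffected; SAP 6.2 only inherits a figure that cannot be reproduced.

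Finally, the cited PK study may report the missing CVs. The documents do not, and that is the extent of the claim.

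**Conclusion.** The point holds. With the inputs printed in SAP 2.3 and the synopsis, 84 per group at CV 0.330 gives 99.5% per test and about 93% over the 15 tests, against 98% to 99.0% and 81% stated. The per-test gap is small; the study-wide gap is about 12 points, and no dependence among the tests closes it. The 81% fits a common CV of about 0.362 by product, or unreported CVs near the top of the stated range.

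This does not show the trial to be underpowered. At 0.330 the printed power is conservative, and in the least favourable case examined within the stated range, with Cmax at 26.3%, the product is 79% and the simulated values are 82% to 89%. The three unreported CVs and the endpoint correlations are assumptions, and all figures take the true ratio as 1.000, as the plan does.

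**What to change.** Amend SAP 2.3, the synopsis and Protocol 6.1 so that they agree:

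- State the CV used for each of the five co-primary endpoints, with its source.
- Recompute and restate the power per test and for all 15 tests at those CVs.
- Say how the 15 tests were combined: a product of per-test powers, or a joint simulation with the assumed correlation.
- Remove 0.330, or correct it and its percentage label.

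The cost is text only. Enrolment, the analysis and the decision rule do not change.

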### 2.4. RANDOMIZATION

In Part A, patients will be randomized in a 1:1:1 ratio to receive the first course of SAIT101 (n=94) versus Rituxan® (n=94) versus MabThera® (n=94). The first course includes two intravenous (i.v.) 1,000 mg study drug infusions: one on Day 1 (Visit 2) and the second on Day 15 (Visit 5).

Document: \\ieedc-vnasc01\Biosdata\Archigen\SAIT101\YWA21301\Biostatistics\Documentation\SAP  
 Author: Version Number: V2.0  
 Version Date: 13Feb2019

Template No: CS\_TP\_BS016 Revision 4 Reference: CS\_WI\_BS005  
 Effective Date: 01Apr2016

In Part B, eligible patients in the SAIT101 arm or MabThera® arm will receive the second course of SAIT101 treatment or MabThera®, respectively, at Week 24 and Week 26, however, in the Rituxan® arm will be randomized in a 1:1 ratio to receive SAIT101 or Rituxan® treatment at Weeks 24 and 26. The second course includes two 1,000 mg i.v. infusions (one at Week 24 and the second infusion at Week 26 [14 days later]) of study drug.

At Week 24, patients will be evaluated for further course of the infusion, i.e. Part B.

## 2.5. SCHEDULE OF EVENTS

The schedule of events is provided in Table 2 in the protocol.

## 2.6. CHANGES TO ANALYSIS FROM PROTOCOL

Summary for Change from Baseline in DAS28-ESR at Week 8, 16, 24, 36 and 52 will be added. Comparison between SAIT101 and Rituxan® will be added as exploratory analyses in [section 15.2.5](#).

Definition of depletion in CD19+ B cell count was updated from CD19+ B cell count below 14/ $\mu$ L to CD19+ B cell count below 20/ $\mu$ L, because the assay limit reported by the central laboratory is 20 cells/ $\mu$ L.

To evaluate differences among Mexican site 10703 and all other sites between baseline characteristics, additional tables of baseline characteristics will be added by site 10703 vs other sites in [section 9](#).

Two additional impact analyses will be added for PK in [section 13.2](#) and one will be added for main efficacy analysis in [section 15.2.7](#).

The study will be unblinded until Week 52, instead of Week 24 in protocol, per sponsor decision.

There will be no interim analysis and CSR prepared based on the 24-week data of all patients. Analysis of Part A and Part B will be combined into one final analysis.

Additional analyses for immunogenicity have been added in [section 17](#), per sponsor decision.

